9.4. Withdrawal of participants

Subjects are free to discontinue participation in the investigation at any time, and without prejudice to further treatment. Subjects who discontinue the investigation should always be asked about the reason(s) for their discontinuation and about the presence of any Adverse Event/Adverse Device Effect or Device Deficiency and, if possible, be assessed by an investigator. Adverse Event/Adverse Device Effect should be followed up.

Subjects may be withdrawn from investigation treatment and assessments at any time, at the discretion of the investigator.

Incorrectly enrolled subjects will be withdrawn from further investigation treatment and assessments. A subject may, however, continue the investigation under special circumstances (i.e. if continuation of investigation treatment or follow-up actions are necessary for the subject's safety and well-being, or if only a follow-up period remains, and the continuation of the investigation is not expected to be associated with any risk or discomfort for the subject)

10. INVESTIGATIONAL DEVICE

10.1. Investigational device details

The following devices are used within the clinical investigation:

Product	Product name	Reference number	Disposable/ reusable	CE- marked/ registered
EVA cassette	EVA Cartridge with 0.5 L Collection Bag	8100.CAR01	Disposable	Yes
Dual Air Fluid Tubing	Disposable FVA Air Fluid, Dual Tubing		Disposable	Yes
VGPC Input Set	Disposable EVA VGPC Input Set	8110.VGP01	Disposable	Yes
23G Vitrectome	Disposable High Speed TDC Cutter 23 G / 8000 CPM DORC Continuum range	8268.VIT23	Disposable	Yes
23G Light fiber shielded wide	Shielded TotalView Endoillumination Probe, including illuminated scleral depressor.(23 gauge / 0.6 mm)	3269.SBS06	Disposable	Yes
23G Trocar set	Disposable One step Cannula System.(23 gauge / 0.6 mm)	1272.ED206	Disposable	Yes
23G Laser fiber	Directional Laser Probe with DORC connector.(23 gauge / 0.6 mm)	7223.DORC	Disposable	Yes
25G Vitrectome	Disposable High Speed TDC Cutter 25 G / 8000 CPM DORC Continuum range	8268.VIT25	Disposable	Yes
25G Light fiber shielded wide	Shielded TotalView Endoillumination Probe, including illuminated scleral depressor.(25 gauge / 0.5 mm)	3269.SBS05	Disposable	Yes
25G Trocar set	Disposable One Step Cannula System (25 gauge/0.5 mm)	1272.ED205	Disposable	Yes
25G Laser fiber	Directional Laser Probe with DORC connector.(25 gauge / 0.5 mm)	7225.DORC	Disposable	Yes
27G Vitrectome	Disposable High Speed TDC Cutter 27 G / 8000 CPM DORC Continuum range	8268.VIT27	Disposable	Yes
27 Light fiber shielded wide	Shielded TotalView Endoillumination Probe, including illuminated scleral depressor.(27 gauge / 0.4 mm)	3269.SBS04	Disposable	Yes
27G Trocar set	Disposable One step Cannula System.(27 gauge / 0.4 mm)	1272.ED204	Disposable	Yes
27G Laser fiber	Laser Probe, Stepped, Curved with DORC [®] Connector 27 gauge / 0.4 mm	7527.DORC	Disposable	Yes
Phaco handpiece*	Phaco Sure Touch Handpiece	3002.P	Reusable (steam sterilized)	Yes
Phaco needle*	EVA Custom Phaco Pack VGPC 2.2 mm Triple step angled flared phaco needle with 45 degrees tip	8510.22AF2	Disposable	Yes
Membrane Blue Dual liquid	MembraneBlue Dual	MBD-05-S	Disposable	Yes
ILM Blue Liquid	ILM-Blue	ILMB-05-S	Disposable	Yes

*Other phaco handpiece or needles (i.e. larger or different angle) are allowed

All of the above device are presently in use in the UZLeuven for daily vitrectomy surgery. Hence, there is no need for any dedicated device or instrument in this clinical trial.

10.2. Device manufacturer

Manufacturer of devices included in section 10.1 is D.O.R.C. Dutch Ophthalmic Research Center (International) B.V., [name], The Netherlands.

10.3. Device accountability

Devices used for each surgery will be documented. In the hospital, there is a standard procedure for returning faulty products. This procedure will be followed, similar to the standard clinical path.

10.4. Storage conditions

All disposable devices come pre-sterilized and will be used before expiration date. The reusable instruments will be steam-sterilized according to the guidelines provided by the manufacturer.

10.5. Concomitant Treatments

Before, during and after the surgery, the same medication and antiseptic treatment will be applied as in patients following the standard clinical path. This includes:

- Preoperative application of mydriasert to dilate the pupil
- Preoperative antiseptic treatment with betadine
- BSS plus infusion liquid during the surgery
- Injection of parabulbar triamcinolone and clindamycin at the end of the surgery
- Postoperative dexamethasone anti-inflammatory eyedrops

At the discretion of the investigator, additional medication may be prescribed.

11. CLINICAL INVESTIGATION ASSESSMENTS

11.1. Subject Characteristics

The following parameters will be collected:

- 1. History: prior eye surgery (excluding previous vitrectomy)
- 2. Surgical parameters:
 - Indication of the surgery
 - Anesthesia type: local / general / local with sedation / general with parabulbar
 - Technique: 23G, 25G or 27G
 - Combined phacovitrectomy: yes / no If yes: Phaco power used: Total phaco time, effective phaco time and average phaco power
 - Surgery time:
 - \circ $\;$ total time of surgery
 - $\circ \quad \text{phaco time} \quad$
 - \circ vitrectomy time
 - peeling time
 - Tamponade(s) used (only air allowed)
 - Diathermy applied (Yes/No)
 - Phaco femto applied (Yes/No)
 - Cryo applied (Yes/No)
 - Laser applied (Yes/No)
 - Vital dyes used: yes/no If yes: type:
 - ILM peeling performed: yes/no

PVD created: yes/no

- Vitreous stain used: yes/no If yes: Type:
- Anticoagulants used by subject: recorded in the eCRF in list of concomitant medication(s):
 - Yes/No
 - o Type
 - Stopped: Yes/No
 - Time stopped
- Medications used:
 - Preoperative disinfection:
 - Preoperative preparation (dilation drugs):
 - $_{\odot}$ $\,$ Infusion liquid use:
 - Additives in infusion liquid:
 - Intra-operative: intra-cameral or intravitreal medication
 - Postoperative:
 - Parabulbar:
 - Topical:
 - General:
- Actions required to close the eye at the end of the surgery
 - o None
 - Sclerotomy massage
 - Sclerotomy squeezing
 - $\circ \quad \text{Injection of air bubble}$
 - \circ Suturing of the sclerotomy
 - If yes: number of sutures placed
- Adverse events during surgery^{6,7,8,9}:
 - Phaco:
 - Zip in capsulorhexis
 - Posterior capsule tear
 - Vitreous prolapse
 - Iris prolapse
 - Dropped nucleus
 - Vitrectomy:
 - o Iatrogenic retinal tear
 - Lens touch
 - o Choroidal hematoma
 - Infuse subchoroidal
 - Iatrogenic retinal damage
 - Subretinal haemorrhage
 - o Iris trauma
 - Retinal incarceration
 - PFCL subretinal
 - Oil subretinal
 - Hemorrhage from retinal vessel
 - Hemorrhage from choroid
- 3. Postoperative parameters:
 - Amount of pain during the first 24 postoperative hours (using pain scale)
 - Visual acuity day 1 postoperative

- Intra-ocular pressure day 1 postoperative
- Slit-lamp examination day 1 postoperative: flare and cells in the anterior chamber
- Photograph of the external eye to assess reddishness and swelling of eyelids

[figure not shown]
4. Questionnaire

To be completed by the patient about postoperative morbidity during the first postoperative week

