4. CLINICAL INVESTIGATION SUMMARY

Title	Comparative study 27G to larger gauge vitrectomy		
Reference Number (Acronym)27G compared to larger gauge sizes			
Clinical Phase	Post-Market stage		
Objectives	To perform a prospective randomized comparison of postoperative recovery between 27G and larger gauge surgical approaches		
Endpoints	Primary endpoint: determine whether ultra-small gauge surgery (27G) improves postoperative outcome and patient morbidity		
Design	Investigator-initiated, comparative double-arm, mono-center, prospective, interventional case study		

Data Collection	Total duration of study for each patient will be 1 week or less (from surgery to last follow-up). See Study Flow Chart 7.3
Planned Clinical investigation Period	2020-2021
Clinical investigation population	Patients that are scheduled for a vitrectomy surgery for either floater removal or macular surgery, with or without combined cataract (phaco) surgery.
Number of Participants	Target 500 patients
Inclusion/Exclusion Criteria	 Inclusion criteria Patients aged over 18 No prior vitrectomy surgery in the study eye (for the same eye) No prior inclusion in this trial Scheduled for vitrectomy for floater removal or macular surgery (including macular holes) without endotamponades such as PFCL, Gas or Silicone oil. Air tamponade is allowed. Exclusion criteria Patients with serious heart, lung, liver, or kidney dysfunction Patients with proliferative diabetic retinopathy, endophthalmitis, uveitis, eyes with refraction >+5D or <-8D, or other eye disease that impacts the outcome of vitrectomy surgery Patients with history of drug abuse or alcoholism Patients participating in other drug or medical device clinical trials before screening for this trial Pregnancy, preparation for pregnancy during clinical trial, or breast-feeding Belief by the investigator that a patient's condition would hinder the clinical trial, such as a patient prone to mental stress, loss of control of mood, or depression
Device Name	EVA used in combination with a trocar system, light fiber, vitrectome and laser fiber either in 27G or larger gauge sizes. In case of a combined surgery also a phaco hand piece and phaco needle are used.
Principle Intended Use	All devices are used within their claimed intended use. In general, all devices are intended to be used during ophthalmic surgery.
Manufacturer Name	D.O.R.C. Dutch Ophthalmic Research Center (International) B.V.

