6. OBJECTIVES

6.1 Primary objective

The primary objective and primary endpoint are shown in the table below:

Primary objective	Primary endpoint
The aim of this study is to perform a prospective randomized comparison of postoperative recovery between the 27G and larger gauge surgical approach. Patients will be randomized to be operated using 27 gauge or a larger	The outcome of the trial is to prospectively determine whether ultra- small gauge surgery (27G) improves postoperative outcome and patient morbidity.
gauge size.	 For this purpose, the following postoperative parameters will be used: Post-operative redness (Eye Photo) Ophthalmic examination including biomicroscopy to evaluate the amount of intra-ocular inflammation.

The secondary objective and secondary parameters are shown in the table below:

Secondary objective	Secondary endpoint
To obtain additional outcome parameters for both the 27 gauge and larger gauge surgery	Postoperative parameters: - Visual Acuity (LogMAR BCVA) - Intra-ocular pressure (mmHg) - Pain assessment (Questionnaire with visual analogue scale)

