7.2 Study diagram

7.3 Study Flowchart

	Day 0: Surgery	Day 1 Postoperative (+/- 0 days)	Week 1 Postoperative (+/- 2 days)
Surgery	Х	0	0
Visual Acuity	0	Х	0
Pain assessment	0	Х	0
Intra-Ocular Pressure	0	Х	0
Slit lamp	0	Х	0
Eye photo	0	Х	0
Questionnaire	0	0	Х

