11.4.1 Adverse events that do not require reporting

After vitrectomy, the following transient adverse events are commonly present during the first week after surgery, hence will not require reporting:

- Decreased visual acuity compared to preoperative measurement
- Reddish eye
- Increased ocular pressure
- Mild to moderate intra-ocular inflammation
- Mild corneal edema

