¹ (a) Missing Completely At Random (MCAR): the missingness pattern is independent from observed and unobserved data; (b) Missing At Random (MAR): conditional on the observed data, the dropout is independent of the unobserved measurement; and (c) Missing Not At Random (MNAR): when neither MCAR nor MAR hold, the missingness depends on the observed, as well as on the unobserved data.

Morris, 2013) and mixed models for discrete data will be used to model binary outcomes (Kahan & Harhay, 2015).

For demographic and baseline data, continuous data will be compared by means of T-test when homogeneity of variances, tested with the Bartlett's test, and normality of the residuals, tested with the Shapiro-Wilks test, will be reached and means and standard deviations (means \pm StDev) will be reported. When homogeneity of the variance or normality of the residuals won't be proved, Wilcoxon signed rank test will be performed on rank data and medians and inter-quartile ranges (median [Q₂₅ - Q₇₅]) will reported. For count data, the Pearson Chi-Squared test will be performed to compare proportions. We will use the software R, version 3.6.2 or above (R Core Team, 2017) to perform the statistical analyses.

Hedeker D, Gibbons RD (2006). Longitudinal Data Analysis. Wiley-Interscience, Hoboken, NJ.

Kahan, B.C. & Haray, M.O. (2015). Many multicentre trials had few events per centre, requiring analysis via random-effects models or GEEs. Journal of Clinical Epidemiology, 68(12), 1504-1511.

Kahan, B.C. & Morris, T.P. (2013). Analysis of multicentre trials with continuous outcomes: when and how should we account for centre effects? Statistics in Medicine, 32(7), 1136-1149.

Rubin DB. Inference and missing data. *Biometrika*.1976;63:581–592.

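### Acuity and pressure are listed on day 1 only and no baseline covariate is named for their comparison: a small, cheaply avoided loss of precision on two secondary endpoints

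*Combined protocol and SAP*

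**What the plan says.** The secondary endpoints in section 6 include "Visual Acuity (LogMAR BCVA", pressure in mmHg and pain. In the list of data to be collected (section 11.1), acuity and pressure appear among the postoperative parameters, as "Visual acuity day 1 postoperative" and "Intra-ocular pressure day 1 postoperative". The flowchart in section 7.3 has columns for surgery, day 1 and week 1 but none for screening. Its acuity row and its "Intra-Ocular Pressure" row are marked at day 1 only. Section 4 describes the study period thus: "Total duration of study for each patient will be 1 week or less (from surgery to last follow-up".

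Two places point the other way. Section 11.4.1 exempts from reporting "Decreased visual acuity compared to preoperative measurement", which presupposes that a preoperative acuity exists. Section 13.1 states: "For demographic and baseline data, continuous data will be compared by means of T-test", although section 11.1 lists no demographic items. No section mentions a preoperative pressure.

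On analysis, section 13.1 names Wilcoxon-Mann-Whitney tests for the primary outcomes and, for continuous outcomes, mixed models with centre as a random effect. Baseline data are compared between arms but not used to adjust a treatment effect. Section 13.1 says that multiple imputation can also fill in covariates, without naming any. Section 13.5 can bring a covariate into the model, but only because it predicts missingness. Section 13 restricts comparisons to the two arms within a centre, and section 13.2 sets 25 patients per arm at each site.

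**The concern.** Acuity and pressure differ between patients before surgery. If the preoperative value predicts the day-1 value, a day-1 comparison that ignores it carries avoidable noise. With only 25 per arm in each comparison, precision is scarce, and a chance difference between arms at baseline can colour a single site's result. The plan names no model that would remove either effect. The covariate rule in section 13.5 does not fill the gap, because it selects on missingness and not on prognosis.

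What is at stake is the sharpness of two secondary comparisons. The primary outcomes (cells, flare and redness) and their tests are not affected.

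**Working it through.** **The plan's own figure.** There is none to reproduce here. The sample sizes in section 13.2 concern cells, flare and redness, and the pilot category percentages behind them are not given.

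**Inputs.** From the documents: 25 per arm, so N = 50 per comparison (section 13.2); two-sided 5% with adjustment for multiple comparisons (section 13.3). Assumed: the correlation r between the preoperative and day-1 value, shown from 0 to 0.7; a true difference of 0.8 SD; and a two-sample t-test as the unadjusted comparison, since section 13.1 names no within-centre test for these endpoints.

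**Step 1: bias.** In 20,000 simulated trials with 25 per arm, complete data and a true difference of 0.50 SD:

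| r | mean, unadjusted | mean, ANCOVA | SD of estimate, unadjusted | SD of estimate, ANCOVA |
|---|---|---|---|---|
| 0.3 | 0.502 | 0.502 | 0.28 | 0.273 |
| 0.5 | 0.499 | 0.500 | 0.28 | 0.247 |
| 0.7 | 0.499 | 0.498 | 0.28 | 0.204 |

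Both methods are centred on the truth. Only the spread differs.

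**Step 2: relative efficiency.** With p covariates, ANCOVA relative to the unadjusted comparison is worth

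(N − 3 − p) / (N − 3) / (1 − r²) = (46/47) / (1 − r²) for N = 50 and p = 1.

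- r = 0: 0.979 / 1 = 0.98
- r = 0.2: 0.979 / 0.96 = 1.02
- r = 0.3: 0.979 / 0.91 = 1.08
- r = 0.5: 0.979 / 0.75 = 1.30
- r = 0.7: 0.979 / 0.51 = 1.92

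Break-even is where 1 − r² = 46/47, so r = √(1/47) = 0.146.

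**Step 3: power for a 0.8 SD difference, 25 per arm.** Power is about 79% unadjusted at two-sided 5%. If a Bonferroni correction over the three secondary endpoints is assumed (0.05/3 = 0.0167), it is about 64%. ANCOVA changes these as follows; the figures are good to about one point.

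| r | at 5% (from 79%) | at 0.0167 (from 64%) |
|---|---|---|
| 0 | 78% | 63% |
| 0.2 | 80% | 65% |
| 0.3 | 82% | 67% |
| 0.5 | 89% | 77% |
| 0.7 | 97% | 92% |

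Put as the difference detectable with 80% power at two-sided 5%: 0.81 SD unadjusted, against 0.82, 0.78, 0.71 and 0.58 SD with ANCOVA at r = 0, 0.3, 0.5 and 0.7.

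**Step 4: chance imbalance.** The baseline difference between arms has SD √(2/25) = 0.283 baseline SD. A difference of at least 0.4 SD in either direction therefore has probability 2 × [1 − Φ(0.4/0.283)] = 0.157, or about 16% of sites. This averages to zero over repetitions but affects a single site's reading.

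**The case against.** The strongest reply is that nothing here is shown to be broken. Section 11.1 is not a complete list: it omits demographic data that section 13.1 says will be compared. Its silence on preoperative values is therefore weak evidence, and the case report form (Appendix C) is not shown. This stands. A reader might infer that preoperative acuity and pressure are not collected; the documents support only that they are not listed.

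Second, the benefit depends on an unknown r. Section 11.4.1 treats reduced acuity and raised pressure as common and transient in the first week, and air tamponade and combined phaco are allowed. Such disturbance could push r down, into the range where the gain runs from −2% to +8% (r = 0 to 0.3). This also stands as a possibility, which is why the range starts at zero. The worst case is small, and break-even is only about r = 0.15.

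Third, these endpoints are secondary and unpowered, and section 13.6 leaves the final statistical plan open until before data lock and before any analysis. That limits the point to a minor one. It does not remove it, because the final plan is where the covariate should be named.

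A reader might also infer that combined phaco and indication should enter the models, or that redness needs a rank test stratified by phaco. The material does not carry this. Within a site, cells and flare gain essentially nothing. The stratified redness test loses power unless phaco shifts the score by about 0.4 SD or more, an effect that the documents do not give. The larger gains appear in models pooled over centres, which sections 12.3 and 13 rule out. The conflict between those sections and the cross-centre models in section 13.1 is a separate matter.

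**Conclusion.** The point holds as a modest loss of precision on two secondary endpoints. Acuity and pressure are listed on day 1 only, and no baseline covariate is named for comparing them between arms. Whether the preoperative values are captured is not settled by the documents.

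The size rests on the assumed r: from a 2% loss at r = 0 to the equivalent of 1.92 times the patients at r = 0.7, per site. The power levels also depend on how section 13.3's multiplicity adjustment is applied to the secondary endpoints; the relative efficiencies do not.

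A reader might infer that the unadjusted comparison is biased. With randomisation and complete day-1 data it is not. The condition matters. In an assumed example with about 9% missing, where missingness depends on the preoperative value differently by arm, a true 0.50 SD difference becomes 0.52 to 0.57 SD in an unadjusted complete-case analysis for r from 0.3 to 0.7. The documents give no dropout rate and no sign of such a pattern, so this is a further reason to have the baseline value but not a finding of bias.

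Severity: minor, a cheap improvement.

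**What to change.** 1. Confirm that preoperative LogMAR acuity and, where on file, preoperative pressure are in the eCRF; if they are not, add them. Make sections 7.3 and 11.1 say so.
2. State in section 13.1 that day-1 acuity and pressure are compared between arms within each centre by ANCOVA on that one preoperative value, with missing baselines handled by the multiple imputation already planned there.
3. Keep the unadjusted Wilcoxon-Mann-Whitney test for the primary outcomes, and add no phaco or indication covariates or stratified test on account of this point.

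The cost is at most two eCRF fields and a sentence or two of analysis text, with no extra visit for values already on file. Consent is signed on admission on the day of surgery (section 9.2), so the values will mostly come from the routine file; some may be missing and some acuities may not be in LogMAR. If the baseline proves not to be prognostic, about 2% of precision is lost.

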11.2. Clinical investigation assessments

Patients that are scheduled for vitrectomy surgery that is commonly performed either 23G or 27G instruments will be included. The preoperative preparation of the patient and the surgery itself will not be different from the standard of care. In the postoperative period, some additional examinations will be performed on the first postoperative day:

• The patient will be asked to grade the amount of postoperative pain experienced (using a pain scale as below)

- A photograph will be taken from the outside eye, and the amount of reddishness will be graded by and independent observer. See annex A. Photos to be made without flash, with eyes looking in all directions (e.g. 4 directions with lid up and down) and distance chosen such to have the eyes on photo with subjects not recognizable.
- A questionnaire will be given to the patient upon discharge from the hospital with questions to assess the postoperative recovery. The patient will be asked to mail us these questions back after one week.
- 1. Are you self-employed / employed/ retired / disabled / other:
- 2. Did you sleep less well during the first night after surgery due to eye pain? Yes / No $\,$
- 3. Did you sleep less well during the first week after surgery due to eye pain? Yes / No
- 4. Did you wake up during the first night due to eye pain? Yes / No
- 5. Did you wake up during the first week due to eye pain? Yes / No
- 6. Did you take pain medication during the first night after surgery due to eye pain? Yes / No
- Did you take pain medication during the first week after surgery due to eye pain? Yes / No
- Did you use an eye cream after the surgery during pain or abrasive feeling? Yes / No

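### First-night sleep, waking and pain-medication answers are scheduled only on a form mailed back after a week, although pain for the same period is scored on day 1

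*Combined protocol and SAP*

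**What the plan says.** Three items of the patient questionnaire in Section 11.2 concern the first night:

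- item 2: "Did you sleep less well during the first night after surgery due to eye pain"
- item 4: "Did you wake up during the first night due to eye pain"
- item 6: "Did you take pain medication during the first night after surgery due to eye pain"

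All three are yes/no. They share one form with items about the first week. On handing it out, 11.2 says: "A questionnaire will be given to the patient upon discharge from the hospital with questions to assess the postoperative recovery". On getting it back: "The patient will be asked to mail us these questions back after one week". The flowchart in 7.3 has a single mark for the questionnaire, in the week-1 column, which has a window of two days either side.

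Day 1 has no window. The flowchart schedules visual acuity, pressure, slit lamp, eye photograph and the pain assessment there. Section 11.1 defines the pain item as "Amount of pain during the first 24 postoperative hours (using pain scale". Pain is a secondary endpoint, listed in Section 6 as "Pain assessment (Questionnaire with visual analogue scale".

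Section 11.1 also provides for a concomitant-medication list in the eCRF, mentioned in connection with anticoagulants, and for postoperative medication under parabulbar, topical and general headings. Neither has a stated analgesic item or a time of intake.

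**The concern.** On day 1 the patient already answers a question about the first 24 hours. The other first-night questions wait for a mailed form, so their completeness depends on postal return instead of attendance at a scheduled visit. Two things are at stake.

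First, the plan asks whether 27G surgery improves patient morbidity, and these items are direct patient reports of it. Each unreturned form removes them, and return may depend on how recovery went.

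Second, a pain score is easier to interpret beside analgesic use over the same period. If patients in the more painful arm take more medication, the observed difference in pain is smaller than it would be without it. The plan does not pair the two measures. Their periods also differ: item 6 covers the first night, the scale covers 24 hours.

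**Working it through.** No figure in the documents bears on this point, so there is none to reproduce. The sample-size table in 13.2 concerns cells, flare (tyndall) and redness only. The check is a comparison of sections, followed by an illustration on assumed rates.

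**Where first-night information can enter the data**

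- Sleep and waking: items 2 and 4 only, marked at week 1 in 7.3. No day-1 item covers them.
- Analgesic use as reported by the patient: item 6 only, on the same form.
- Analgesic use as recorded by staff: possibly the general postoperative and concomitant-medication fields in 11.1. These could hold prescribed or in-hospital drugs. Nothing there asks for analgesics, times them, or links them to the pain score. Section 11.3 allows outpatient treatment, so some patients spend the first night at home.
- Recovery of a missing form: Section 9.4 asks patients who stop for their reasons, adverse events and device deficiencies, not for the form. No reminder is described.
- Missing-data methods: 13.1 plans maximum likelihood and multiple imputation in general terms, and 13.5 defines the missingness check for the primary outcome. No imputation model for these items is given.

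**Loss of precision.** Inputs: 25 patients per arm per site (13.2) and an assumed non-return r of 10%, 20% or 30%. The standard error is multiplied by 1/√(1 − r).

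- r = 10%: 25 × 0.10 = 2.5 forms lost per arm; 1/√0.90 = 1.05
- r = 20%: 25 × 0.20 = 5 forms lost per arm; 1/√0.80 = 1.12
- r = 30%: 25 × 0.30 = 7.5 forms lost per arm; 1/√0.70 = 1.20

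As an example of power within one site, take assumed rates of 50% and 20% on a yes/no item, with two-sided alpha 0.05 and the normal approximation. Power is 0.61 with 25 forms per arm, 0.55 with 22, 0.51 with 20 and 0.47 with 18. These are the full-return, 10%, 20% and 30% cases, with the number of forms rounded.

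**Bias in a single rate.** Suppose 30% truly took medication, and 70% of users and 90% of non-users return the form. The observed rate is 0.3 × 0.7 / (0.3 × 0.7 + 0.7 × 0.9) = 0.21/0.84 = 25%. With 60% return in users it is 0.18/0.81 = 22%.

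**Bias in the comparison between arms.** Observed odds in an arm equal true odds × (return in users / return in non-users). Hence observed odds ratio = true odds ratio × the ratio of that factor between arms.

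- Same return pattern in both arms (70% and 90%): the factor is 0.7/0.9 = 0.778 in each arm and cancels. With true rates of 50% and 20%, the observed rates are 0.35/0.80 = 43.8% and 0.14/0.86 = 16.3%. The odds ratio is 4.0 before and after. The risk difference moves from 30 to 27.5 points. If the true rates are equal, the observed rates are equal too.
- Return pattern different by arm (70% and 90% in one arm, 90% and 90% in the other), with a true rate of 30% in both: observed 25% against 30%. The odds ratio is (0.25/0.75)/(0.30/0.70) = 0.78 where the truth is 1.

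Outcome-dependent return alone therefore does not bias the odds ratio. It has to differ by arm.

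**The case against.** A single take-home form covering the whole first week is a coherent choice, and most of the case against this point limits its reach.

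- A reader might infer that analgesic use is unknown. The documents do not support that, because 11.1 has medication fields that may capture part of it. What stands is that no analgesic item, timing or link to the pain score is specified, which matters most for drugs taken at home.
- A reader might infer that every patient who stops after day 1 loses these answers. The form is handed over at discharge, so such a patient can still send it in. What stands is that nothing in the plan retrieves it.
- A week's recall is not certain. Section 11.2 fixes when the form is mailed, not when each item is answered, and a patient may fill in the first-night items the next day. Recall of up to a week is possible, and the plan does not prevent it.
- For every returned form, item 6 can be joined to the pain score at analysis, so a late arrival does no harm in itself. This is right. The remaining issues are non-return, recall and the mismatch between one night and 24 hours.
- Pain as experienced, whatever medication was taken, is a legitimate randomised comparison. It understates a difference only if the arm with more pain also medicates more, and the documents do not show that this will happen.
- Section 7.1 counts three visits, which might suggest that the form could be collected in person at week 1. Section 11.2 describes mail, however, and 7.3 places no other assessment at that time.

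**Conclusion.** The gap is real and of minor to moderate weight. The first-night sleep and waking items, and the patient's own report of first-night pain medication, have no planned collection point before the week-1 form, although a visit covering the same period is already scheduled. Analgesic use is not specifically captured or timed when pain is scored.

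The size depends on a return rate that the documents do not give. At an assumed 10% to 30% non-return, standard errors for these items rise by 5% to 20%. A stronger reading, that the treatment comparison on these items is biased, is not supported: on the odds-ratio scale it requires return to depend on arm as well as on the answer, and the documents give no evidence either way.

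Redness and intra-ocular inflammation, the primary parameters, are collected on day 1 and are untouched. The pain score is also taken on day 1 and is not lost. The three items are not named individually in the endpoint tables.

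**What to change.** - Ask items 2, 4 and 6 at the day-1 visit beside the pain scale. Keep them self-completed, so that the mode of answering does not change and the answers do not pass through staff who may know the gauge.
- Word item 6 to cover the same 24 hours as the pain scale.
- Leave the first-week items (3, 5 and 7) and the eye-cream item on the mailed form.
- Mark the questionnaire at day 1 as well as week 1 in 7.3.
- State in Section 13 that the day-1 pain score will be reported together with the proportion using pain medication in the same window, by arm.

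The cost is about a minute more at day 1 and a revised form. No visit is added. First-night answers should then be about as complete as the day-1 pain score. The change records analgesic use but does not remove its effect on the score, so the paired report is descriptive.
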